**Table 10.1-1: Study Event Schedule**

Assessment	Screeninga	Baseline	Procedure	Within 1 Day Post-procedure	Prior to Discharge or 7 Days Post-Procedure	30 Daysb (±7 Days) Office Visit	12 Monthsb (±30 Days) Office Visit	24–60 Monthsb [Annual] (±45 Days) Office Visit	84 and 120 Monthsb (±60 Days) Office/In person Visit	72, 96, and 108 Monthsb (±60 Days) Telephone
-------------------	------------------------------	-----------------	------------------	------------------------------------	--	---	--	--	--	--

Abbreviations: AE=adverse event; ADE=adverse device effect; AKI=acute kidney injury; BAV=balloon aortic valvuloplasty; CBC=complete blood count; CEC=Clinical Events Committee; CK-MB=creatin kinase-myoglobin band; CRC=Case Review Committee; CT=computed tomography; CV=cardiovascular; ECG=electrocardiogram; EOA= effective orifice area; LDH=lactate dehydrogenase; LV=left ventricle; MRI=magnetic resonance imaging; mRS=modified Rankin Scale; NIHSS=National Institutes of Health Stroke Scale; NYHA=New York Heart Association; QOL=Quality of Life; SAE=serious adverse event; SADE=serious adverse device effect; STS=Society of Thoracic Surgery; TEE=transesophageal Doppler echocardiography; TTE=transthoracic Doppler echocardiography; UADE=unanticipated adverse device effect; VARC=Valve Academic Research Consortium

## 10.2. Study Candidate Screening

Subjects will be evaluated for eligibility by the center heart team (which must include an experienced cardiac interventionalist and an experienced cardiac surgeon). The heart team should take into account the Society of Thoracic Surgeons (STS) score as well as other clinical comorbidities (including frailty) not accounted for in the risk calculation. Eligible subjects will have agreement from the heart team that the subject is at intermediate operative risk of mortality with SAVR (see **Table 8.2-1** for inclusion criteria). Risk of operative mortality and morbidity is to be assessed via an in-person evaluation by a center cardiac surgeon and must be confirmed by the CRC (which must include an experienced cardiac surgeon). The heart team must also agree that the subject is likely to benefit from valve replacement.

Clinical assessment and evaluation, collected tests and images (e.g., echocardiography, computerized tomography [CT], angiography) performed in preparation for TAVR, and any planned use of balloon aortic valvuloplasty (BAV) will be reviewed by the CRC (see Section 7.2 and Section 21.2). The CRC will be comprised of experienced cardiac surgeons, interventional cardiologists, and Sponsor staff proficient with the LOTUS *Edge* Valve System and will confirm subject eligibility for enrollment.

### 10.2.1. Strategies for Recruitment and Retention

The REPRISE IV study will include subjects presenting with documented severe native aortic valve stenosis who are indicated for TAVR (see Section 8). It is estimated that nearly 5% of elderly  $\geq 75$  years of age have aortic stenosis and its prevalence is expected to increase due to an aging population. Because aortic stenosis most commonly occurs in the very elderly, women are well represented in TAVR trials. Traditionally underrepresented populations (elderly and women) are expected to be included in the subject population as allowed by governing law/national regulation; as the very elderly will represent the majority of subjects enrolled in the trial, efforts to maximize retention are by definition targeted to traditionally under-represented groups. The inclusion and exclusion criteria are not expected to have a negative effect on recruitment or retention of said populations. In the United States, the subjects eligible for inclusion in this study are likely to be Medicare patients due to their expected age and the results of this study are likely to be highly generalizable to a Medicare population.

All efforts will be made to minimize attrition in REPRISE IV (see Section 9.4). Investigators are encouraged to enroll subjects who are willing to comply with the follow-up requirements of the study. If a visit is missed, the center should attempt to contact the subject to reschedule the missed visit and counsel the subject on the importance of maintaining the assigned visit schedule.

### 10.3. *Subject Informed Consent*

Informed consent (see Section 20) must be obtained from a potential subject prior to conducting any preoperative assessments that are not part of the local routine preparation and evaluation of a subject for TAVR, even if the subject's eligibility has not yet been completely determined.

The Investigator/designee, who has been trained on the protocol, will explain the nature and scope of the study, potential risks and benefits of participation, and answer questions for the subject. If the subject agrees to participate, the IRB/HREC-approved ICF must be signed and personally dated by the subject or his/her legally authorized representative. The Investigator/designee must also sign the ICF prior to subject enrollment. Any additional persons required by the center's IRB/HREC to sign the ICF must also comply. Study personnel should explain to the subject that even if the subject agrees to participate in the study and signs the ICF, the heart team and/or the CRC may determine that the subject is not a suitable candidate for the study and/or TAVR procedure.

If during the course of the preoperative evaluations, the subject is found not to be eligible for inclusion in the study, the subject should be notified. Reason for ineligibility will be accounted for as "screening failure" and will be documented as such in the eCRF screening module. If the subject has signed the ICF but is found not eligible for inclusion in the study prior to or during the procedure, the subject should receive the appropriate treatment as identified by the clinical investigator. Information regarding the screening failure will be captured on the screening module and subject will be included in the "screening cohort" accountability.

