	
AEC2. Subject has atrial fibrillation that cannot be rate controlled to ventricular response rate < 60 bpm.
 
AEC3. Subject is expected to undergo chronic anticoagulation therapy after the index procedure.
 
Note 10: Subjects treated with short-term anticoagulation post procedure can be included in the imaging substudy; in these subjects the 30-day imaging will be performed 30 days after discontinuation of anticoagulation.

Statistical Methods	
Analysis Sets	
Analysis sets are listed below.
 
 
- Intention-To-Treat (ITT): This population includes all subjects who sign an Informed Consent Form and are enrolled in the study, regardless of whether the study device is implanted.
 
- Implanted: This population includes all subjects who sign an Informed Consent Form, are enrolled in the study, and are implanted with the study device.
 
 
A subject is considered enrolled in the study when an attempt is made to insert a LOTUS Edge valve.

Primary Endpoint Statistical Hypothesis	
In the Main Cohort, the rate of the primary endpoint (composite of all-cause mortality and all stroke at 1 year) is less than the performance goal (PG) of 15.2% (expected rate of 11.1% plus testing margin of 4.1%).

Statistical Test Method for the Primary Endpoint	
A one-sample z-test will be used to test the one-sided hypothesis that the 1-year primary endpoint rate for LOTUS Edge in the Main Cohort is less than the PG:
 $H_0: P_{\text{LOTUS Edge}} \geq \text{PG}$ $H_1: P_{\text{LOTUS Edge}} < \text{PG}$ 
where <math>P_{\text{LOTUS Edge}}</math> is the primary endpoint rate for the LOTUS Edge group and PG is the performance goal.
 
The primary analysis set for the primary endpoint is the ITT analysis set. This endpoint will also be analyzed for the implanted analysis set.

REPRISE IV: REpositionable Percutaneous Replacement of Stenotic Aortic Valve through Implantation of LOTUS Edge™ Valve System in Intermediate Surgical Risk Subjects	

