## 9. Subject Accountability

### 9.1. *Point of Enrollment*

Subjects who are confirmed eligible for the study by the CRC (see Section 21.2) and who provided written informed consent are considered enrolled in the study as soon as an attempt is made to insert the LOTUS *Edge* Valve System into the subject's femoral artery.

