#### 11.1.1.4. Statistical Methods – Primary Endpoint

All subjects who are enrolled will be eligible for evaluation. Handling of dropouts and missing data will depend on their frequency and the nature of the outcome measure. Sensitivity analyses (e.g., tipping-point analysis) will be performed to assess the impact of subjects with inadequate follow-up (i.e., missing data) on the primary endpoint and to assess the robustness of the conclusion of the primary analysis. Statistical models that account for censored data will be employed in appropriate circumstances (e.g., for time-to-event outcomes). Suspected invalid data will be queried and corrected in the database prior to statistical analysis. Additional information may be found in the statistical analysis plan (SAP).

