### **11.2.1. Analysis Sets**

The primary endpoint and additional measurements will be analyzed on an ITT and an implanted basis. For ITT analyses, all subjects who sign the IRB/HREC-approved study ICF (see Section 10.3) and are enrolled in the trial will be included in the analysis, whether or not a study valve was implanted. For implanted analyses, ITT subjects who had the study valve implanted will be included in the analysis.

For the Main Cohort, the primary endpoint will be analyzed for the ITT and implanted analysis sets. The primary analysis for the primary endpoints will be based on the ITT analysis set.

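### Section 10.3's screening-failure rule has no cut-off at the LOTUS Edge insertion attempt, so from that attempt to the end of the procedure it conflicts with the enrollment and ITT rules

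*Combined protocol and SAP*

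**What the plan says.** Section 10.3 (Subject Informed Consent) deals with loss of eligibility after consent: "If the subject has signed the ICF but is found not eligible for inclusion in the study prior to or during the procedure", the subject receives whatever treatment the investigator judges appropriate. It continues: "Information regarding the screening failure will be captured on the screening module", with the subject counted in the screening cohort. It gives no cut-off within the procedure and no cross-reference to Section 9.1.

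Section 9.1 (Point of Enrollment) says that consented subjects confirmed by the Case Review Committee are "considered enrolled in the study as soon as an attempt is made to insert the" LOTUS Edge Valve System into the femoral artery. The synopsis has the same rule.

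Section 11.2.1 (Analysis Sets) puts into ITT all subjects who sign the consent form and "are enrolled in the trial will be included in the analysis, whether or not a study valve was implanted". Section 11.1.1.4 adds: "All subjects who are enrolled will be eligible for evaluation".

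Section 19.1 requires event reporting from the same insertion attempt. Section 10.10 follows enrolled subjects without a study device for 1 year and implanted subjects for up to 10 years.

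**The concern.** The procedure does not end at the insertion attempt. If ineligibility comes to light after it, Section 9.1 says the subject is enrolled and Section 10.3 says the subject is a screening failure. An example is anatomy within EC20 or EC21 that becomes apparent only when the catheter will not advance.

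The direction of any resulting error is predictable. The decision would be made at the site, with the course of the procedure known, in a single-arm trial with no blinding and a fixed performance goal. Subjects whose procedures went badly are likely to have more deaths and strokes than the rest. Losing them would lower the observed primary endpoint rate and raise the rate of successful access, delivery and deployment. The tipping-point analysis in Section 11.1.1.4 addresses enrolled subjects with inadequate follow-up, so it would not reach someone never recorded as enrolled.

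**Working it through.** **Step 1. Set the rules against the order of events in Section 10.7.**

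| Stage | Sections 9.1, 11.2.1, 19.1 | Section 10.3, if found ineligible | Result |
|---|---|---|---|
| Introducer placed, optional valvuloplasty, hemodynamic and rhythm check | Not yet enrolled | Screening failure | Consistent |
| Insertion attempt through advancement, position check, resheathing or retrieval, and closure | Enrolled, in ITT, events reportable | Screening failure ('during the procedure') | Conflict |
| After the procedure | Enrolled, in ITT | Not addressed | Consistent |

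The conflict arises in the second row only if 'during the procedure' extends past insertion. The protocol uses the phrase that way elsewhere: Sections 4, 4.2 and 18.5 all describe a decision, taken during the procedure, not to implant and to retrieve the valve. That decision can only follow insertion.

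**Step 2. Reproduce the design (Section 11.1.1.2).** Inputs: p0 = 0.152, p1 = 0.111, one-sided α = 0.025, power 87.5%, attrition 3%.

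n = [(1.960·√(0.152·0.848) + 1.150·√(0.111·0.889)) / 0.041]² = [(0.7037 + 0.3614) / 0.041]² = 674.8, so 675. Then 675/0.97 = 695.9, so 696. Both stated figures reproduce, and the wording conflict does not affect them.

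**Step 3. Find the pass mark.** The z-test passes if x/675 < 0.152 − 1.960·√(0.152·0.848/675) = 0.1249, that is, with at most 84 events. The exact type I error is P(X ≤ 84 | 675, 0.152) = 0.0239.

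**Step 4. Remove m enrolled subjects with event rate e when the true ITT rate equals the goal.** Expected events are 675 × 0.152 = 102.6. The remaining rate is (102.6 − m·e)/(675 − m). The pass mark c is recomputed at 675 − m, and the type I error is the binomial tail up to c. Both m and e are assumptions.

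| m | e | n left | Rate left | c | Type I error |
|---|---|---|---|---|---|
| 3 | 30% | 672 | 15.13% | 83 | 0.0228 |
| 3 | 40% | 672 | 15.09% | 83 | 0.0246 |
| 7 | 30% | 668 | 15.04% | 83 | 0.0305 |
| 7 | 40% | 668 | 14.94% | 83 | 0.0360 |
| 12 | 30% | 663 | 14.93% | 82 | 0.0337 |
| 12 | 40% | 663 | 14.75% | 82 | 0.0445 |

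The flat result at m = 3 partly reflects discreteness: the pass mark drops to 83 at n = 672, where the exact error at 15.2% would be 0.0204. It still does not exceed the nominal 0.025.

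**Step 5. Look at the boundary.** With 85 events in 675 the test fails (z = −1.89). Removing one subject with an event gives 84/674 and it passes (z = −1.98). With 86 events, two such removals are needed; with 87, four.

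**Step 6. Ask what the documents say about m and e.** RESPOND (Section 4.1.2.3) enrolled 1014 and had 996 as-treated. That gap of 18 (1.8%) scales to 12 of 675. On RESPOND's reported ITT denominator of 1005 the gap is 9, which scales to 9/1005 × 675 = 6. RESPOND's 30-day deaths were 26/1005 in ITT and 22/996 as-treated. If the as-treated set is nested in the ITT set, 4 of the other 9 died, so a 30–40% rate by 1 year is not extreme. However, RESPOND enrollment rested on consent and selection for the valve, not on an insertion attempt. Neither figure measures what is needed here.

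**The case against.** The strongest reply is that enrollment and ITT membership are fixed elsewhere and Section 10.3 cannot undo them. It sits in the consent section and never mentions analysis sets. Sections 9.1, 11.2.1 and 11.1.1.4 keep every subject with an insertion attempt in ITT, implanted or not. Sections 10.10 and 19.1 already require 1-year follow-up and event reporting. Catheter insertion times (Section 10.7) and device-use records (Section 15.1) would leave a trace of any inserted device. All of this stands.

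A reader might therefore infer too much: that the plan allows enrolled subjects to be taken out of ITT after a failed delivery, and that their follow-up and event reporting lapse. The documents do not support that. The trigger in 10.3 is ineligibility, not failed delivery. Section 10.7 has a separate provision for an unsuccessful transfemoral approach that does not send the subject to screening failure. Eligibility is also confirmed beforehand by the Case Review Committee from core-laboratory CT.

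There is also a harmless reading of 10.3, because introducer placement and valvuloplasty precede LOTUS Edge insertion. It is possible but unstated, and the protocol's own use of the phrase for post-insertion decisions tells against relying on it. The ITT definition can protect only subjects recorded as enrolled, and 10.3 is an instruction about how to record them.

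On size, successful access, delivery and deployment was 120/120 in REPRISE II. Technical success was 21/21 in REPRISE NG DS Cohort C and 100% in REPRISE EDGE, though 5/7 in Cohort B. Few subjects may ever be in this position, and not all of them would be reclassified.

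**Conclusion.** Wrong as written: an internal conflict. For a subject found ineligible between the insertion attempt and the end of the procedure, Section 10.3 and Sections 9.1, 11.2.1 and 19.1 give opposite answers, and no passage ranks them. ITT should govern, and the protocol contains no rule permitting post-enrollment exclusion. The defect is that a site following 10.3 literally could record one.

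The effect is probably small and cannot be estimated from the documents. The range of about 2.3% to 4.4%, against an exact 2.4%, assumes that 3 to 12 enrolled subjects are all reclassified, that they have a 30–40% event rate, and that the true ITT rate equals the goal. Three removals give no material inflation, and 12 is toward the upper end. The delivery success rate would be affected in the favourable direction, by an amount the documents do not allow one to state. Sample size and planned power are unaffected.

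**What to change.** In Section 10.3, replace 'prior to or during the procedure' with: *before an attempt is made to insert the LOTUS Edge Valve System (Section 9.1)*.

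Then add: *A subject found ineligible after that attempt remains enrolled and in the ITT set, is followed on the schedule that applies to implanted or non-implanted subjects, and the finding is recorded as a protocol deviation.*

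The follow-up clause should point to the existing schedules and not name 1 year, because such a subject may have been implanted and implanted subjects are followed for up to 10 years.

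The cost is a short wording change in the protocol and matching eCRF guidance, with no change to sample size or procedures. The downside for the sponsor is that the observed event rate and delivery success rate may be slightly less favourable.

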### 10.4. *Screening Assessments*

Results from the screening tests and procedures listed below must be submitted to the CRC (see Section 21.2) for evaluation to confirm a subject's eligibility for the study. Screening assessment documentation should be provided via electronic upload at least 5 days in advance of a scheduled CRC review or at least 5 days in advance of the planned procedure date. It is planned that CRC reviews will take place at least weekly or as needed to ensure timely review and confirmation of subject eligibility.

**Note 1:** It is recommended that predilatation be performed unless there is minimal calcification of the annulus and leaflets. Subjects in the bicuspid registry must have predilatation performed.

**Note 2:** Additional concomitant procedures, including percutaneous coronary intervention, are not allowed during the index procedure.

Centers will be trained on the screening process (see Section 16.4.2). Specific data points will be collected in the REPRISE IV electronic case report forms (eCRFs) as shown below.

- Clinical assessments
  - Demographics including age and gender

- Medical history (general medical; cardiac [including previous cardiac surgery]; neurological, renal [including creatinine] and peripheral disease; and other medical conditions)
- Physical examination including weight and height
- NYHA classification
- Current antiplatelet and other cardiovascular medications
- 12-lead electrocardiogram (ECG) at screening must be performed according to the ECG Core Laboratory guidelines (see study Manual of Operations) and, if subject is enrolled, forwarded to the core laboratory for analysis
- Risk assessments: Society of Thoracic Surgeons (STS) score, euroSCORE II, heart team assessment including an in-person evaluation by a center cardiac surgeon and any frailty assessments (detailed in next bullet).
- Frailty, disability, and comorbidity assessments (collected prospectively)
  - Body Mass Index from the physical exam
  - Strength and balance
    - Use of wheelchair
    - Gait speed as measured by a stopwatch for a subject to walk 5 meters (3 measures averaged)
    - Number of falls in the past 6 months
    - Maximal grip strength (kg) in the dominant hand (3 measures averaged), using a hand-held dynamometer
  - Activities of daily living: Katz Index is based on an evaluation of the functional independence or dependence of a subject in bathing, dressing, going to toilet, transferring, continence, and feeding. A point is assigned for independence in each of the 6 functions, and 0 points if there is any dependence in these 6 categories.
- Imaging assessments
  - Within 60 days prior to CRC approval, TTE (2-D, M-Mode, and color) must be carried out. The evaluation should include assessment of effective orifice area (EOA), peak and mean aortic valve gradient pressure, aortic regurgitation assessment, mitral regurgitation, LVEF, left ventricular end-diastolic and end-systolic diameter, tricuspid regurgitation (TR) jet velocity, and left atrial (LA) volume. The TTE must be performed according to the Echocardiography Core Laboratory procedure guidelines (see study Manual of Operations). For enrolled subjects, the TTE must be provided to the echocardiography core laboratory for independent analyses. In cases of low flow/low gradient aortic stenosis with left ventricular dysfunction (ejection fraction <50%), dobutamine can be used to assess the grade of aortic stenosis (maximum dobutamine dose of 20 mcg/kg/min recommended); the subject may be enrolled if echocardiographic criteria are met with this augmentation. In cases where a subject who has met the echocardiographic

criteria for enrollment receives BAV prior to the index procedure and subsequently no longer meets the REPRISE IV aortic valve pressure gradient or EOA criteria, the subject may still be enrolled based on the pre-BAV echocardiographic data. In such cases, the most recent echocardiogram done prior to the index procedure (even if after BAV) must be submitted to the Echocardiography Core Laboratory to be included in the baseline data.

- A coronary angiogram/CT coronary angiogram must be performed within 365 days prior to CRC approval. If there is concern regarding the current extent of coronary artery disease or aortic stenosis, the CRC may recommend a repeat study closer to the time of enrollment. An aortogram and hemodynamics including simultaneous ascending aorta and left ventricle pressure measurements should be performed.
- A CT angiogram of the aortic complex must be performed 180 days prior to CRC approval (and should be performed within 90 days if possible) to evaluate the aortic valve anatomy and aortic root dimensions to determine eligibility and device sizing. It must meet the CT Core Laboratory procedure guidelines (see study Manual of Operations) and be provided in advance to the core laboratory for detailed measurements and independent analyses, which will be reviewed by the CRC to confirm a subject's eligibility.
- An assessment of the iliofemoral system must be performed within 180 days prior to CRC approval (and should be performed within 90 days if possible). A CT angiogram of the iliofemoral system should be performed for complete visualization of the iliac and femoral arteries to assess for dimensions, tortuosity, and calcification. The CT angiogram of the iliofemoral system should be performed per the procedure guidelines (see study Manual of Operations) and provided to the CT Core Laboratory with the screening CT angiogram of the aortic structure for independent measurements and review by the CRC to confirm a subject's eligibility. An iliofemoral invasive angiogram may be substituted for the iliofemoral CT angiogram.

